6.5 Sample Size and Power

For Aim 1, assuming a mortality rate of 16% and a PARDSEVERE sensitivity of 0.85 and specificity of 0.65, the sample size needed for two-sided 95% CI width of ≤ 0.16 (i.e., sensitivity of 0.85 with 95% CI 0.77 to 0.93) is 454 subjects. In our single-center study of 152 subjects and 16% mortality [45], our sensitivity was 0.96 and specificity was 0.66, suggesting that these assumptions are realistic. We have increased this to 500 total subjects with samples collected to account for ~10% of subjects being unevaluable due to sample loss or degradation during transport and storage.

For the transcriptomic Aims 2 and 3, we anticipate 475 evaluable subjects with sufficient RNA from the total cohort of 500 subjects with samples collected, assuming a conservative estimate of 5% drop-out due to neutropenia. As we found evidence for ARDS endotypes in our preliminary cohort of 67 subjects, we anticipate adequate numbers for endotype discovery. As a comparison, in adult sepsis, 4 endotypes were discovered using whole blood gene expression from 306 subjects [50].

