3.3.2 Total Number of Study Sites/Total Number of Subjects Projected

The study will be conducted at 16 investigative sites in the United States.

Recruitment will stop when 500 subjects are enrolled with samples collected. It is expected that up to 550 subjects will be recruited to produce 500 evaluable subjects for the plasma biomarker aims, and approximately 475 evaluable subjects for the mRNA aims to account for subjects with only partial samples collected.

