6.4.2 Analysis of Primary Outcome of Interest

For Aim 1, PARDSEVERE biomarker levels will be used to classify subjects according to the previously published PARDSEVERE decision rules without modifications [45]. This allows for assignment of 28-day mortality risk based on allocation of study subjects to one of 5 terminal nodes. Performance of PARDSEVERE will be assessed by AUROC for discriminating 28-day mortality and other diagnostic accuracy measures, including sensitivity, specificity, and positive and negative predictive values at different probability cutoffs. PARDSEVERE will

be considered validated if sensitivity is ≥ 0.85 and specificity is ≥ 0.65 , both with 95% CI width ≤ 0.16 .

For Aim 2, we will perform mRNA gene expression, and identify endotypes using a previously published 100-gene classifier [42, 43].

For Aim 3, we will identify *de novo* endotypes using LCA including biomarker and clinical variables, or novel endotypes using the entire gene expression pattern.

For the transcriptomic part of Aims 2 and 3, the cohort will be split 60:40 into a derivation and test set. In Aim 2, we will determine genome-wide differential gene expression. After filtering and normalizing, gene expression values will be ranked by median absolute deviation across all patient samples. We will then perform unsupervised agglomerative hierarchical clustering on the top 5000 probesets, with clusters allowed $k = 2-12$, as has been done to discover mRNA-based endotypes in adult sepsis [50]. To estimate k (number of endotypes), we will combine cumulative distribution functions and cophenetic distance correlation analysis to assess clustering stability. Using a random forest classifier (supervised classification with high dimensional data methods)[50, 51], we will assess ARDS endotype classification with ten-fold cross-validation of stepwise increments in gene numbers. We will decide on the final number of endotype-defining genes when the process yields a cross-validation misclassification error rate of $< 10\%$.

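### The Aim 1 sample size of 454 does not quite give the stated 95% CI width of 0.16, and sections 3.3.2 and 6.5 disagree on whether 500 means collected or evaluable

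*Combined protocol and SAP*

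**What the plan says.** Section 6.5 (Sample Size and Power) works from "assuming a mortality rate of 16% and a PARDSEVERE sensitivity of 0.85 and specificity of 0.65" and derives "the sample size needed for two-sided 95% CI width of ≤ 0.16". The result is "sensitivity of 0.85 with 95% CI 0.77 to 0.93) is 454 subjects". The loss allowance follows: "We have increased this to 500 total subjects with samples collected to account for ~10% of subjects being unevaluable".

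Section 6.4.2 uses the same width as part of the decision rule. The tool counts as validated if sensitivity is at least 0.85 and specificity at least 0.65, "both with 95% CI width ≤ 0.16". Neither section names the interval method.

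Section 3.3.2 stops recruitment at 500 enrolled with samples collected, then says "up to 550 subjects will be recruited to produce 500 evaluable subjects for the plasma biomarker aims".

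For RNA, section 6.5 says "we anticipate 475 evaluable subjects with sufficient RNA from the total cohort of 500 subjects with samples collected", which is 500 less 5% for neutropenia.

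**The concern.** Sensitivity is a proportion among non-survivors, so its precision depends on the number of deaths, about 16% of the cohort. Putting the plan's inputs into the usual precision formula gives more than 454. The number 500 is also used in two ways. In 6.5 it is collected samples, some of which will be lost; in 3.3.2 it is evaluable subjects after losses.

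The width is the only quantitative basis given for the Aim 1 sample size, and it is one of the conditions for declaring the tool validated. A reader should be able to reproduce the number, know how many evaluable subjects are planned, and know which interval will be held against 0.16.

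**Working it through.** **Inputs.** From 6.5: two-sided 95% (z = 1.96), sensitivity 0.85, specificity 0.65, mortality 16%, loss about 10%. From 6.5 and 6.4.2: width at most 0.16, so half-width 0.08.

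**Step 1: the plan's own figure.** By Wald, deaths needed = z² × p(1 − p) / h².

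- Deaths = 1.96² × 0.85 × 0.15 / 0.08² = 76.5.
- Subjects = 76.5 / 0.16 = 478.3, so 479. With deaths first rounded up, 77 / 0.16 = 481.25, so 482.

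The stated 454 is not reproduced. Other intervals do not return it either (N without and with deaths rounded up):

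| Interval | N for width ≤ 0.16 |
|---|---|
| Jeffreys | 472 / 475 |
| Wilson | 477 / 482 |
| Wald | 479 / 482 |
| Logit | 492 / 494 |
| Agresti-Coull | 496 / 500 |
| Exact (Clopper-Pearson) | 545 / 550 |
| Wald, continuity-corrected | 554 / 557 |

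A half-width of 0.0821 does give 454: 1.96² × 0.1275 / 0.0821² / 0.16 ≈ 454.2. Its limits, 0.768 and 0.932, round to the printed 0.77 and 0.93. Two-decimal rounding is thus a plausible source, but that is an inference.

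**Step 2: specificity is not limiting.** 1.96² × 0.65 × 0.35 / 0.08² = 136.6 survivors, and 136.6 / 0.84 = 162.6, so 163 subjects. At 450 subjects its width is 0.096.

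**Step 3: the loss allowance.** 454 × 1.10 = 499.4, which matches the 500. To retain 454 after a 10% loss takes 454 / 0.90 = 504.4, so 505. In the other direction, 500 × 0.90 = 450. Read loosely, 454 of 500 is a loss of 46 / 500 = 9.2%. Section 6.5 therefore leaves about 450 to 454 evaluable. In 3.3.2, going from 550 to 500 is a loss of 50 / 550 = 9.1%, taken between recruitment and the evaluable set.

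**Step 4: expected width for sensitivity 0.85.**

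| Evaluable N | Expected deaths | Wald | Wilson | Exact |
|---|---|---|---|---|
| 450 (6.5, 10% loss) | 72.0 | 0.165 | 0.165 | 0.177 |
| 454 (6.5, as stated) | 72.6 | 0.164 | 0.164 | 0.176 |
| 482 | 77.1 | 0.159 | 0.159 | 0.171 |
| 500 (3.3.2) | 80.0 | 0.156 | 0.156 | 0.167 |

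**Step 5: the 6.4.2 rule with whole deaths.** The rule also needs observed sensitivity of at least 0.85.

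- 72 deaths: 61/72 = 0.847 fails on the estimate. The next result, 62/72 = 0.861, has width 0.1598 (Wald) or 0.1599 (Wilson) and passes.
- 73 deaths: 63/73 = 0.863 has width 0.158 by both and passes.
- 71 deaths: 61/71 = 0.859 has Wald width 3.92 × √(0.859 × 0.141 / 71) = 0.162 and fails on width.
- 74 deaths: 63/74 = 0.851 has Wald width 3.92 × √(0.851 × 0.149 / 74) = 0.162 and fails on width.
- Exact interval: 62/72 gives 0.172 and 63/73 gives 0.170; both fail on width.

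**The case against.** The strongest reply is that the discrepancy is slight. The widths at 450 and 454 exceed 0.16 by 0.005 and 0.004, and their limits agree with the printed interval at two decimals. Width also shrinks as observed sensitivity rises. With 72 deaths the Wald width is within 0.16 from a sensitivity of about 0.861, and at the 0.96 seen in the single-center study it would be about 0.09. All of this stands, and it limits the importance of the point. It does not make 454 the answer to the stated requirement.

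A reader might go further and infer that the plan is bound to miss its precision target. The documents do not support that. Section 3.3.2 plans 500 evaluable for the plasma aims, and there Wald and Wilson meet the target.

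A reader might also infer that Aim 1 would fail its own rule even if the tool performs as assumed. Step 5 does not bear that out as a general statement. At 72 or 73 deaths, the smallest result that passes on sensitivity also passes on width by Wald or Wilson. Width can decide the matter at 71 or 74 deaths, or with an exact interval, so the criterion is not idle.

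Finally, a reader might infer that the 475 for RNA is wrong because the 10% loss was left out. That loss is stated in the Aim 1 paragraph, RNA is drawn into a separate tube with its own handling (5.1.2.2), and nothing says the two losses combine. The odds-ratio calculation at 475 in 6.4.2 is explicitly for reference and not what the study is powered on.

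**Conclusion.** The figure of 454 is wrong as written. With the plan's inputs and a Wald interval the requirement is 479 evaluable subjects, or 482 with 77 whole deaths, so 454 is about 5 to 6% low (454 / 479 = 0.948; 454 / 482 = 0.942). By the exact interval it is 545 to 550. No standard interval tried gives a width of 0.16 or less at 454.

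Whether the study as planned reaches the target is unsettled. It narrowly misses on section 6.5 (0.164 to 0.165 by Wald or Wilson). On the 500 evaluable of section 3.3.2 it meets the target by Wald or Wilson (0.156) and misses it by the exact interval (0.167). These are expected widths at 16% mortality and sensitivity 0.85; the realized width will vary with both. The shortfall is small and does not by itself make Aim 1 fail. It deserves correction because the same width sets the sample size and enters the validation rule.

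**What to change.** - **6.5:** replace 454 with 479 to 482 evaluable subjects (about 77 deaths) and name the interval, Wald or Wilson. Compute the allowance as N / (1 − loss): 479 / 0.90 = 533 and 482 / 0.90 = 536 collected.
- **6.4.2:** name the same interval for the validation rule. Leave the 0.16 criterion as it is; loosening it to suit the sample would be hard to defend.
- **3.3.2 and 6.5:** state whether 500 is collected or evaluable, and at which stage the 10% is lost.
- **If 500 collected is kept:** state the expected width as about 0.165 at 450 evaluable.
- **If 500 evaluable is meant and 10% of collected samples are lost:** 500 / 0.90 = 556 must be collected. That exceeds both the stop at 500 collected and the 550 expected to be recruited, so it is an operational change.
- **RNA:** at most, add a sentence saying whether the transport and storage loss also applies to the 475.

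Keeping 500 collected costs only wording and a slightly less favorable precision statement. Any option that collects more than 500 changes the recruitment stop.

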7 SAFETY MANAGEMENT

7.1 Clinical Adverse Events

Clinical adverse events (AEs) will be monitored throughout the study.

7.2 Adverse Event Reporting

Since the study procedures are not greater than minimal risk, SAEs are not expected. If any unanticipated problems related to the research involving risks to subjects or others happen during the course of this study (including SAEs) these will be reported to the IRB in accordance with CHOP IRB SOP 408: Unanticipated Problems Involving Risks to Subjects. AEs that are not serious but that are notable and could involve risks to subjects will be summarized in narrative or other format and submitted to the IRB at the time of continuing review.

8 STUDY ADMINISTRATION

8.1 Data Collection and Management

For patients who meet eligibility criteria, the parents or legal guardians will be approached for study enrollment. The site PIs or trained staff members will engage them in a discussion regarding reasons for the study, the study procedures, and the risks and benefits and answer all questions. Due to the critical nature of the patients' conditions in the PICU, this discussion may take place at the patient's bedside or in an alternative location (e.g., family conference room) at the parent/guardian's option and the study investigator's discretion. All reasonable safeguards to ensure patient privacy will be taken. Parents/guardians will be given sufficient time (i.e., up to several hours) to decide whether or not to participate in this study. Following the above conversation seeking informed consent from each patient's parent/guardian and obtaining agreement from the parent/guardian to participate in this study, we will provide a copy of the combined consent-HIPAA authorization document to the parent/guardian and patient.

We also have a waiver of assent for all patients. Given the inclusion criteria of invasive mechanical ventilation, and the necessary associated sedation, we do not anticipate any instances of subjects being able to assent.

Paper versions of all CRFs will be kept on-site in a locked office. Data will be entered into web-based online CRF (Redcap) that will be password-protected. Only study personnel authorized by the IRB will have access to study-related data and files, and have password access to the online CRF.

Confidentiality will be assured by keeping the list containing personal health identifiers (PHI) and subject ID restricted to the individual sites, such that the only data submitted to CHOP is limited in PHI (site, dates of ARDS, demographic information) and coded with a subject ID number. Furthermore, all downloaded study-related data will be kept in encrypted, password-protected files on the PI's desktop computer in a locked office, with password-protected back-ups on the Departmental share drives for research. [name] (PI) and study personnel authorized by the IRB will have access to this data.

Specific consent will be obtained to store blood and use data for future research, which will be explicitly recorded. There will be plans to share this data with the research community using the Biologic Specimen and Data Repository Information Coordinating Center (BioLINCC) program at NHLBI, and we will follow suggested guidelines for de-identifying the data (coding of site IDs, conversion of dates to study days).

Pursuant to the NIH position that sharing of resources (such as this study) is an important means to enhance the value of NIH-sponsored research, all data obtained from this proposal will be made readily available for research by qualified individuals within the scientific community after publication of the proposed studies. Gene expression data from Aims 2 and 3 will be made available simultaneous with publication of the results of these aims by uploading to the Gene Expression

Omnibus, consistent with the NIH Genomic Data Sharing Policy. For dissemination of plasma biomarker results and the associated clinical dataset, we will use the Biologic Specimen and Data Repository Information Coordinating Center (BioLINCC) program at NHLBI, with release of a de-identified dataset with appropriate untraceable identifiers within 2 years of publication of the main manuscript, alongside a detailed mechanism of how to request data samples. As we intend to use a layered consent, with an option to opt out of future studies, we will ensure this information is conveyed to BioLINCC.

8.1.1 Data sources

Data will be collected by trained research staff from the patient's inpatient chart. In the majority of cases, we anticipate this being an electronic medical record, rather than a paper chart.

8.2 Confidentiality

All data and records generated during this study will be kept confidential in accordance with Institutional policies and HIPAA on subject privacy. The Investigator and other personnel will not use such data and records for any purpose other than conducting the study.

Confidentiality will be assured by keeping the list containing personal health identifiers (PHI) and subject ID restricted to the individual sites, such that the only data submitted to CHOP is limited in PHI (site, dates of ARDS, demographic information) and coded with a subject ID number. Furthermore, all downloaded study-related data will be kept in encrypted, password-protected files on the PI's desktop computer in a locked office, with password-protected back-ups on the Departmental share drives for research. [name] (PI) and study personnel authorized by the IRB will have access to this data.

No identifiable data will be used for future study without first obtaining IRB approval. The investigator will obtain a data use agreement between provider (the PI) and any recipient researchers (including others at CHOP) before sharing a limited dataset (demographics, dates).

8.3 Regulatory and Ethical Considerations

8.3.1 Data and Safety Monitoring Plan

All data and records generated during this study will be kept confidential in accordance with Institutional policies and HIPAA on subject privacy and that the Investigator and other site personnel will not use such data and records for any purpose other than conducting the study. Confidentiality will be assured by keeping the list containing personal health identifiers (PHI) and subject ID restricted to the individual sites, such that the only data submitted to CHOP is limited in PHI (site, dates of ARDS, demographic information) and coded with a subject ID number. Furthermore, all downloaded study-related data will be kept in encrypted, password-protected files on the PI's desktop computer in a locked office, with password-

protected back-ups on the Departmental share drives for research. All study-related files will be secured on password-protected drives.

All blood specimens will be collected and stored using tubes labeled with a study ID number. Any remaining blood specimens following study measurements will be stored in a coded manner after obtaining specific informed consent to store these specimens and use for future research purposes. No identifiable data or PHI will be used for future study without first obtaining IRB approval.

8.3.2 Risk Assessment

The risks for patients participating in this study are not greater than minimal risk and include those related to 1) blood collection for study measurements and 2) breach of confidentiality. There is no other practical way to collect data for the proposed research.

Risks related to blood collection: The volume of blood collection will be limited to 6.1 mL per one-time draw in all subjects. In any patient whose clinical condition might be adversely affected by removal of the stated blood volume for this study (e.g., patients with significant anemia or compromised cardiac output), we will discuss further limiting the volume of blood withdrawn for research purposes with the patient's attending physician. Any patient concurrently enrolled in another study for whom enrollment in this study would mean the combined blood volume collection would exceed IRB regulations will be excluded from this study and the reason for exclusion noted. Finally, since patients with ARDS typically undergo multiple blood draws per day, whenever possible blood sampling for study purposes will be timed with other clinically indicated lab draws in order to limit access to indwelling vascular catheters.

Risks related to breach of confidentiality: Extensive efforts will be taken to protect this information including storage of downloaded data in an encrypted, password-protected desktop, and keeping the majority of the PHI at the respective sites, with only a limited dataset utilizing unique study IDs used for the majority of data analyses. PHI will be removed as soon as is practical after data collection. If families choose not to participate, data will not be collected for study purposes. The CHOP IRB requires annual updates for continuing approval for all studies, and the CHOP Office of Research Compliance and Regulatory Affairs performs routine audits of all protocols.

8.3.3 Potential Benefits of Study Participation

Pediatric ARDS carries substantial morbidity and mortality, with no directed therapies available. Guidelines for management are often extrapolated from adult ARDS, despite the distinct epidemiology and outcomes in pediatric ARDS. Studies specifically investigating the mechanisms underlying pediatric ARDS are needed. The proposed studies will lay the foundation for improved risk stratification of pediatric ARDS, and potentially for the identification of specific sub-populations which may benefit from trials of targeted therapies. While there are no direct benefits to patients as a result of participation in this study, these indirect benefits for future pediatric patients with ARDS may lead to improved outcomes.

8.3.4 Risk-Benefit Assessment

Given the minimal risk profile associated with this study, the overall benefits to science, pediatric medicine, future generations of children with ARDS, and society as a whole clearly outweigh the risks.

8.4 Recruitment Strategy

Potential study patients will be recruited from the PICU population. All intubated, mechanically ventilated patients will be eligible for screening. Reviewing inclusion and exclusion criteria and confirming eligibility as part of recruitment will involve querying the medical records and discussion with the patient's care team *only*. Potential subjects will not be asked screening questions prior to obtaining informed consent. Since all inclusion and exclusion eligibility criteria will be determined based on clinical documentation in the medical record and no further information about the prospective participant will be required to determine if they are eligible for the research, consent for the recruitment and screening process is not required.

For patients who meet eligibility criteria, the parents or legal guardians will be approached for study enrollment. The site PIs or trained staff members will engage them in a discussion regarding reasons for the study, the study procedures, and the risks and benefits and answer all questions. Due to the critical nature of the patients' conditions in the PICU, this discussion may take place at the patient's bedside or in an alternative location (e.g., family conference room) at the parent/guardian's option and the study investigator's discretion. All reasonable safeguards to ensure patient privacy will be taken. Parents/guardians will be given sufficient time (i.e., up to several hours) to decide whether or not to participate in this study. Following the above conversation seeking informed consent from each patient's parent/guardian and obtaining agreement from the parent/guardian to participate in this study, we will provide a copy of the combined consent-HIPAA authorization document to the parent/guardian and patient.

8.5 Informed Consent/Assent and HIPAA Authorization

For patients who meet criteria, the parents or legal guardians will be approached for study enrollment. The site PI, co-investigators, or trained staff members will engage them in a discussion regarding reasons for the study, the study procedures, and the risks and benefits and answer all questions. Due to the often critical nature of the patients' conditions in the PICU, this discussion may take place at the patient's bedside or in an alternative location (e.g., family conference room) at the parent/guardian's option and the study investigator's discretion. Also, since it is common for parents/guardians to be away from the bedside, we anticipate the need to seek consent over the phone for many patients. Regardless of where this discussion takes place (i.e., in person or via telephone), all reasonable safeguards to ensure patient privacy will be taken. Parents/guardians will be given sufficient time (i.e., up to several hours) to make a decision to participate in this study.

Following the above conversation seeking informed consent from each patient's parent/guardian and obtaining agreement from the parent/guardian to participate in

this study, we will provide a copy of the combined consent-HIPAA authorization document to the parent/guardian and patient.

We will also seek a waiver of assent for all patients, in accordance with regulations 45 CFR 46.408(a).. Given the inclusion criteria of invasive mechanical ventilation, and the necessary associated sedation, we do not anticipate any instances of subjects being able to assent.

